## 7.9. Definition of End of Study

The end of the trial will be when the last participant has been contacted to arrange their final follow-up visit, whether or not the visit takes place.

The trial will be stopped prematurely:

- If mandated by the Ethics Committee;
- following recommendations from the Trial Steering Committee (TSC);
- If review of safety data suggests 1 arm has significant disadvantages to the extent that patient safety is endangered, compared to known standard outcomes for each treatment arm.

The Research Ethics Committee (REC) will be notified in writing if the trial has been concluded or terminated early.

## **8. INTERVENTIONS**

Patients will be randomised to either Partial Ablation (PA) using HIFU or Radical Prostatectomy (RP).

### **8.1. Treatment with Radical Prostatectomy**

Patients randomised to RP will receive this in the form of open, laparoscopic or robot-assisted procedure, according to local centre expertise and clinical judgement. Patients undergoing RP will be listed for surgery optimally within 2 weeks, and no longer than 2 months, unless requested otherwise by the patient.

### **8.2. Treatment with HIFU focal ablation procedure**

HIFU is a relatively new treatment option for patients with prostate cancer and there is some variation in HIFU delivery across sites. In the PART study, patients randomised to the partial ablation arm will have a mandatory 4-6-week rest period following biopsies to allow swelling and inflammation to settle in the prostate, to lower the risk of side effects such as rectal damage. Patients will then be admitted on the day of the procedure or the evening before as appropriate. A phosphate enema will be administered on the morning of surgery to ensure an empty rectum. The type of anaesthesia (regional/ general) will be discussed with the patient and depend on the anaesthetic opinion. The type of anaesthesia chosen will aim to eliminate any patient movement during HIFU treatment to avoid any adverse complications. The patient will be placed in a relaxed lithotomy position. TED stockings and Flowtron boots will be fitted to the patient's legs for prophylaxis against any potential thrombo-embolic event. In accordance with local hospital policy sub-cutaneous heparin may be administered peri-operatively. Unless there are any contraindications a dose of 120-160mg of intravenous Gentamicin will be given as antibiotic prophylaxis. A suprapubic catheter will be inserted under cystoscopic guidance before the proposed HIFU treatment. The skin surrounding the supra-pubic entry site should be infiltrated with 10-20cc Bupivacaine 0.5%. The catheter will be placed on gentle traction during the procedure in order to avoid haematuria by strapping to the thigh with adhesive bandage. Should haematuria be evident at the end of the procedure a urethral catheter can be placed to irrigate the bladder whilst in recovery.

Three-dimensional ultrasound images will be taken to allow registration with MRI both pre-treatment and post-treatment in order to evaluate whether the treatment protocol was effective in ablating the lesion. The HIFU probe and machine will be prepared as per the manufacturer's instructions. The probe is covered with a latex protector and primed with degassed water. The HIFU probe is then lubricated with degassed lubricant gel. About 10 to 20mls of this same gel is placed within the rectum. At this point a gentle dilatation of the anus is sometimes required. This is done using one or two digits. Once this is done the probe is introduced into the rectum with as little trauma as possible. Views of the prostate are then obtained to ensure that the images are of high quality and that the proposed therapy is technically feasible. Please refer to the additional Trial Specific Instructions (TSI) relating to the HIFU treatment/re-treatment strategy and training of HIFU clinicians.

## 9. SAFETY REPORTING

### 9.1. Definition of Serious Adverse Events

A serious adverse event is any untoward medical occurrence that:

- results in death
- is life-threatening
- requires inpatient hospitalisation or prolongation of existing hospitalisation
- results in persistent or significant disability/incapacity
- consists of a congenital anomaly or birth defect.

Other 'important medical events' may also be considered serious if they jeopardise the participant or require an intervention to prevent one of the above consequences.

NOTE: The term "life-threatening" in the definition of "serious" refers to an event in which the participant was at risk of death at the time of the event; it does not refer to an event which hypothetically might have caused death if it were more severe.

### 9.2. Reporting Procedures for Serious Adverse Events

Trial centres will use a standardised safety reporting form to inform the Trial Manager of serious adverse events within twenty-four hours of becoming aware of them (initial report). SAEs which may be linked to trial procedures and are unexpected will be recorded as Suspected Unexpected Serious Adverse Reactions (SUSARs) until the end of the study.

Other adverse events which may be linked to trial procedures, but not deemed to be serious, will be recorded as Adverse Reactions (ARs). The causality of SAEs (i.e. relationship to trial treatment) will be assessed by the investigator(s) on the SAE form. All SAEs, SUSARs and ARs will be reviewed by the Chief Investigator, to determine whether the SAE is *related* and *unexpected* as defined by the NRES guidance.

The trial co-ordinating centre is responsible for reporting SAEs, where appropriate, to the Sponsor and ethics committee within required timelines. An SAE occurring to a participant should be reported to the REC that gave a favourable opinion of the study where in the opinion of the Chief Investigator the event was 'related' (resulted from administration of any of the research procedures) and 'unexpected' in relation to those procedures. Reports of related and unexpected SAEs should be submitted within 15 working days of the Chief Investigator becoming aware of the event, using the HRA report of serious adverse event form. OCTRU safety reporting procedures will be followed at all times.

## 10. STATISTICS AND ANALYSIS

### 10.1. Description of Statistical Methods

#### Stage 1:

Stage 1 of the PART study aims to randomise 100 men from 4 centres starting in January 2015, and to achieve an uptake of consent and randomisation of 50% of eligible patients who are invited to take part.

**Stage 2:**

If Stage 1 is successful, we will apply to the HTA for additional funding with the aim of recruiting a further 600-800 additional patients over 5 years (Stage 2) in participating centres (minimum 10) with appropriate skill mix. We will review the statistical power calculations in the light of information from the first 100 patients – in particular, the true incidence of unilateral disease qualifying for PA, the comparative quality of life scores, and primary treatment failure rates. A pragmatic decision will then be made on the final recruitment target. We anticipate that QoL will be better with ablative therapy than radical surgery, particularly functional outcomes such as urinary continence and erectile function, such that an increase of 10% in the primary treatment failure rate (i.e. 25% increased to 35%) might well be considered acceptable to underpin a change in clinical practice. Even allowing for a 10% drop-out rate, 800 randomised 1:1 between PA and RP would provide 80% power at  $2p < 0.05$  to detect a 10% worse treatment failure rate with ablative therapy than radical surgery. If primary treatment failure rates were substantially more than 10% higher with PA than RP then this would be detected with high statistical power enabling a good point estimate of the difference and meaningful subgroup investigations to identify any patient or tumour characteristics that were predictive of treatment failure.

**10.2. The Number of Participants**

Stage 1 of the PART study aims to randomise 100 men with a histological diagnosis of unilateral intermediate risk prostate cancer following a biopsy and mpMRI, between partial ablation of the prostate or RP. If Stage 1 is successful, we aim to randomise a further 700 patients in Stage 2 of the study, though this sample size may be amended in the light of Stage 1.

**10.3. Analysis of Outcome Measures**

Time to primary treatment failure will be analysed by standard logrank methods. Dichotomous variables (such as presence absence of erectile dysfunction) and ordinal variables (such as toxicity grades) will be analysed using Mantel-Haenszel tests. Continuous outcome measures such as quality of life scores will be analysed using independent t-tests or repeated measures regression techniques.

Analysis of healthcare resource use, cost and EQ-5D data - Stage 1

The purpose of the economic analysis in Stage 1 of the PART study is to evaluate the response rate and completion rates of the resource use questionnaires and EQ-5D-5L instrument and to assess the feasibility and usefulness of the self-reported patient resource use diary compared with electronic patient-data capture. A preliminary analysis of the resource-use data and cost-consequence analysis will be used to update the sample size calculations required for Stage 2 of the PART study.

Analysis of healthcare resource use, cost and EQ-5D data - Stage 2*Missing data:*

The resource-use/cost and EQ-5D data will be investigated to ascertain the extent of missing data and whether this is due to random missingness and/or censoring. If this amounts to more than 10% of the data collected missing at random, multiple imputation using standard methods will be undertaken (Rubin and Schenker 1991, Briggs, Clark et al. 2003). The focus of studying the healthcare resource use is to investigate how partially ablative therapies in prostate cancer patients affect the health care costs. With the aim of the economic analysis to estimate how the costs of the intervention minus the difference in health care costs between the intervention and standard treatment (radical prostatectomy) group of patients balances against the health care benefits. An in depth analysis of the healthcare resource use and their costs will be conducted. First the impact of the partially ablative therapies on prostate-cancer specific healthcare resource use/costs (including side-effects, recurrence and progression related costs) will be evaluated over the duration of the study and compared with those arising from radical surgery. Secondly, a regression

framework that relates healthcare costs to baseline characteristics (age, disease stage), progression, side-effects, other co-morbidities and treatment type will be developed. The objective being to provide estimates of healthcare costs for different treatment types, side-effects and disease stages to inform the extrapolation model (see below). A similar regression framework approach will be used for the EQ-5D tariff data at the different data collection time-points, again to inform the extrapolation model.

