### 6.2. Inclusion Criteria

- Men with unilateral clinically significant **intermediate risk** prostate cancer or dominant unilateral clinically significant intermediate risk & small contralateral low-risk disease:
  - Gleason grade score 7 (3+4 or 4+3)
  - High volume Gleason grade score 6 (> 4mm cancer core length)
  - PSA ≤ 20 ng/ml
  - Clinical ≤ T2b disease
- Life expectancy of ≥10 years
- Fit, eligible and normally destined for radical surgery
- No concomitant cancer
- No previous treatment of their prostate cancer
- An understanding of the English language sufficient to understand written and verbal information about the trial, its consent process and the study questionnaires

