#### 7.6. Subsequent Visits

In patients randomised to RP:

1. Routine removal of catheter at **10-14 days**
2. Follow up in the clinic at approximately **six weeks** post-surgery as per routine NHS care. Patients will have had a PSA test prior to their follow-up appointment, the result of which should be available. Quality of life questionnaires will be presented to the patient (see Appendix B).

Followed up in the clinic approximately every **three months** post-surgery in the first year and then approximately every **6 months** as per routine NHS care for 3 years (See Appendix B). Patients will have had a PSA test prior to their follow-up appointment, the result of which should be available. Quality of life questionnaires will be presented to the patient (see Appendix B) If at any point disease progression is suspected (rising PSA  $\geq 0.2$ ) the patient will be restaged.

In patients randomised to PA:

1. Routine removal of catheter at **7 days**
2. **For sites new to performing HIFU, a study specific mpMRI should be performed on the first 5 patients at 2 weeks. These will be centrally reviewed within the Partial Ablation working group.**
3. Followed up routinely at approximately **six weeks** post-surgery as per routine NHS care. Patients will have had a PSA test prior to their follow-up appointment, the result of which should be available. Quality of life questionnaires will be presented to the patient (See Appendix B).
4. Followed up in the clinic approximately every **three months** post-surgery for the first year and then approximately every **6 months** as per routine NHS care for 3 years. Patients will have had a PSA test prior to their follow-up appointment, the result of which should be available. Quality of life questionnaires will be presented to the patient (See Appendix B).
5. Standard care includes an mpMRI at **twelve months**
6. Standard care includes transrectal biopsies at **twelve months**
7. Standard care includes an mpMRI at **three years**
8. Standard care includes transrectal biopsies at **three years**

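### The primary failure comparison is fixed as a plain logrank test; stratifying by baseline Gleason group and PSA would add a modest amount of power at no data cost

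*Protocol*

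**What the plan says.** Section 10.3 names the method for the Stage 2 primary outcome: "Time to primary treatment failure will be analysed by standard logrank methods". It gives no strata or covariates, and section 7.3, which describes the web-based randomisation, lists no balancing factors.

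Section 6.2 admits a range of grades, from "High volume Gleason grade score 6 (> 4mm cancer core length") to "Gleason grade score 7 (3+4 or 4+3"), with PSA up to 20 ng/ml and clinical stage up to T2b. Section 6.3 excludes low-risk and high-risk disease. Histology is discussed at the multidisciplinary meeting before the approach to the patient (7.1). PSA is a baseline assessment (7.4; visit 2 in Appendix B).

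Section 10.1 (Stage 2) sizes the trial on "an increase of 10% in the primary treatment failure rate (i.e. 25% increased to 35"%). It states: "Even allowing for a 10% drop-out rate, 800 randomised 1:1 between PA and RP" "would provide 80% power at" two-sided 5%. The same paragraph mentions baseline factors only for later subgroup work, to "identify any patient or tumour characteristics that were predictive of treatment failure".

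**The concern.** If grade and PSA predict failure, an unstratified logrank compares two mixtures of lower-hazard and higher-hazard men. A test that compares like with like within strata then has more power for the same patients and the same events, and it allows for chance imbalance in those factors. Section 10.1 already looks for baseline characteristics that predict failure, and section 3.2 places 3+4 and 4+3 at different thresholds of clinical significance, yet the named primary test uses neither factor.

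The trial has to show whether ablation fails more often, and by how much, so precision on that comparison matters. The information that would improve it is collected anyway.

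**Working it through.** **1. The plan's own figure.** Inputs from section 10.1: 25% v 35%, two-sided 5%, 80% power, 1:1, 10% drop-out, 800 randomised, so 800 × 0.9 = 720 evaluable (360 per arm).

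- Two proportions, n per arm = [1.96√(2 × 0.30 × 0.70) + 0.842√(0.25 × 0.75 + 0.35 × 0.65)]² / 0.10² = 329, or 658 in all. With continuity correction it is 349 per arm, 698 in all, and 698/0.9 = 776 randomised.
- Power at 360 per arm: 83.5% uncorrected, 81.4% corrected.
- Logrank (Schoenfeld): HR = ln 0.65 / ln 0.75 = 1.497. Events needed = 4(1.96 + 0.842)²/(ln 1.497)² = 193. Events expected = 720 × 0.30 = 216, which gives 84.3% power.

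The stated 800 and 80% therefore reproduce, with a little to spare.

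**2. What stratification adds.** Times were exponential with a 36-month horizon (follow-up "as per routine NHS care for 3 years", section 7.6). Baseline hazards were solved so that overall failure stays at 25% and 35%. The stratified statistic is Z = Σ(O − E)/√ΣV, summed over Gleason group × PSA (10 or less, above 10 ng/ml).

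Assumed, because the protocol does not say: Gleason 6 / 3+4 / 4+3 in 15/60/25%, PSA above 10 in 30%, and the same hazard ratio per Gleason step and for PSA above 10. There were 4,000 trials per row, with a simulation standard error of about 0.6 point per power figure. All tests were run on the same simulated data.

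| Assumed HR per factor | Plain logrank | Stratified | Adjusted Cox | (mean Z ratio)², stratified to plain |
|---|---|---|---|---|
| 1.0 | 83.8% | 83.4% | 83.5% | 0.99 |
| 1.5 | 83.7% | 84.5% | 84.6% | 1.03 |
| 2.0 | 82.2% | 85.9% | 86.0% | 1.10 |
| 2.5 | 85.0% | 90.4% | 90.5% | 1.20 |
| 3.0 (extreme) | 84.0% | 92.3% | 92.3% | 1.31 |

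The last column reads as a relative sample size: 1.10 means that the plain test would need about 10% more men, or 0.10 × 800 = 80.

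**3. Sensitivity to case mix.** With a 20/50/30% Gleason mix, plain v stratified power is 83% v 83% with no effect, 83% v 85% at 1.5, 84% v 87% at 2, and 85% v 90% at 2.5 per Gleason step with 2 for PSA. That mix puts 20% × 70% = 14% of men in the cell Gleason 6 with PSA of 10 or less, which the low-risk exclusion in section 6.3 may thin or empty. Without that cell (3,000 runs) the figures are 84.3% v 84.5% at 1.5, 83.8% v 86.4% at 2, and 84.2% v 88.5% at 2.5 with 2 for PSA.

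**4. The smaller total.** Section 10.1 allows as few as 600 further men, so 700 in all and 630 evaluable. Expected events are 630 × 0.30 = 189, and plain logrank power is 79.3% by Schoenfeld (78.3% by two proportions), before any prognostic effect enters.

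**5. Change of estimand.** To produce the same 25% and 35%, the hazard ratio within strata is 1.509, 1.532 and 1.562 at assumed effects of 1.5, 2 and 2.5, against 1.497 with no prognostic effect.

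**The case against.** The strongest objection is that nothing here is wrong. At 800 randomised the plain test meets its 80% target in every row above. That stands. A reader might infer that the trial is underpowered because it does not stratify, but the documents do not support this. The shortfall just under 80% at 700 men comes from the smaller number, not from omitted covariates. The protocol claims 80% only for 800, and sections 10.1 and 10.2 already provide for the size to be reviewed after Stage 1.

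A reader might also infer that the plain logrank is biased because its hazard ratio sits nearer 1. It is not. Randomisation keeps the test valid, chance imbalance included, and the marginal hazard ratio is a different quantity from the conditional one. The design itself is set on marginal rates.

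The size of the gain rests on inputs that the protocol does not contain. A hazard ratio of 2.5 per Gleason step and 2 for PSA implies a 2.5 × 2.5 × 2 = 12.5-fold range of hazard among men limited to intermediate risk, so a wide prognostic spread cannot be taken for granted. Failure is defined by PSA or clinical progression after surgery, but largely by biopsy, scheduled at 12 and 36 months, after ablation (7.6, 7.8). Grade and PSA need not act equally in the two arms, and the simulated gains may be optimistic. Both points stand, and they limit the size of the claim.

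Lastly, strata are often left to the analysis plan, which is not at hand, and the protocol's wording does not expressly forbid them. Silence on strata would be no finding. But the protocol does name a method, and its ordinary reading is the unstratified test.

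**Conclusion.** The point holds as a modest improvement available without new data. The primary test as named leaves two pre-randomisation factors unused. At 720 evaluable men, stratifying or adjusting would add about 1 power point at an assumed hazard ratio of 1.5 per factor. At 2 it would add about 3 to 4 points (nearer 2 to 3 if Gleason 6 with PSA of 10 or less is excluded). At 2.5 per Gleason step with 2 for PSA it would add about 4 to 5. If the factors are not prognostic the cost is within simulation error.

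These figures assume a case mix, a prognostic strength and a common effect in both arms, none of which the protocol gives. The power statement in section 10.1 is not undermined.

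**What to change.** In section 10.3, make the primary test a logrank stratified by baseline biopsy Gleason group (6, 3+4, 4+3) and baseline PSA (10 or less, above 10 ng/ml), with a stated rule for merging sparse strata. Add any factor used to balance the randomisation. Estimate the hazard ratio from a Cox model adjusted for the same variables. Report the unstratified logrank and the absolute failure rates by arm as supporting results. If a separate analysis plan already sets strata, align the protocol sentence with it.

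The cost is one sentence, fixed before outcome data by arm are examined; the review of power after Stage 1 is a natural occasion. No extra data are needed. The small downside is that the hazard ratio becomes conditional on grade and PSA, which is why the absolute rates should stand beside it.

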## 7.8. Treatment failure

### Radical prostatectomy

In patients receiving RP, primary treatment failure will be defined as a rising serum PSA level reaching  $\geq 0.2\text{ng/ml}$  following initial reduction to  $<0.1\text{ng/ml}$  after surgery; or a failure of serum PSA to reach the level of  $<0.1\text{ng/ml}$  after surgery; or clinical progression to local recurrence/systemic disease.

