### Partial ablation

In patients receiving PA, primary treatment failure will be determined by a combination of repeat prostate biopsies, serum PSA levels and clinical appearance of symptoms/signs suggesting disease progression. Prostate biopsies following PA will determine one of five defined scenarios:

1. negative biopsies, in which case the patient will continue to be followed-up as described;
2. positive biopsy in the originally treated area, in which case the patient will be allowed one additional HIFU treatment before the treatment is classed as having failed;;
3. positive biopsy in the untreated area demonstrating a new focus of intermediate risk disease, in which case the patient will be offered additional partial ablation in this area.
4. positive biopsies in any area of the prostate demonstrating low-risk low-volume disease, in which case the patient will not require additional treatment and follow-up will continue as described;
5. positive biopsy following 2 consecutive treatments in any area of the prostate, in which case the treatment will be deemed as having failed.

If follow-up biopsies demonstrate high-risk disease at any point, this will be considered as primary treatment failure and patients will be offered whole gland treatment according to standard of care.

In the presence of primary treatment failure as described above, the patient will be re-staged using pelvic cross-sectional imaging. Patients will be fully informed of their disease status, grade, clinical stage and the treatment options, such as salvage external beam radiotherapy. Regardless of decisions about additional interventions, patients will continue to be followed up and analysed within the trial in accordance with 'intention-to-treat', with full documentation of subsequent treatments.

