18. APPENDIX A: STUDY FLOW CHART

## 19. APPENDIX B: SCHEDULE OF STUDY PROCEDURES

[figure not shown]
VISITS	1	2	4 (procedure)	5	6	7	8	9	10	11	12	13	14
DAY/MONTH			Day 0	Day 7-14	6W	3M	6M	9M	12M	18M	24M	30M	36M
Give patient PART Patient Information Leaflet (PIL)	X												
Give patient Qualitative Recruitment Investigation PIL & Consent Form	X												
Add patient to screening log	X												
Targeted biopsy (if needed)	X												
PART PIL & Consent Form re-given (if necessary)		X											
Informed Consent		X											
Inclusion criteria		X											
Exclusion criteria		X											
Patient History		X											
Examination		X											
Routine blood tests		X											
PSA blood test		X			X	X	X	X	X	X	X	X	X
Randomisation		X											
Screening log updated		X											
Partial Ablation (ARM 1) or Radical Prostatectomy (ARM 2)			X										
Catheter removal				X									
MRI (HIFU ONLY)				X*					X				X
Biopsy (HIFU ONLY)									X				X
Adverse event reporting			X	X	X	X	X	X	X	X	X	X	X
IIEF-15 Questionnaire		X			X	X	X	X	X	X	X	X	X
IPSS Questionnaire		X			X	X	X	X	X	X	X	X	X
UCLA-EPIC Questionnaire		X			X	X	X	X	X	X	X	X	X
EQ-5D-5L		X			X	X	X	X	X	X	X	X	X
FACT-P Version 4		X			X	X	X	X	X	X	X	X	X
The Modified 18-term Memorial Anxiety Scale Questionnaire		X			X	X	X	X	X	X	X	X	X
Resource Utilisation Questionnaire (patient diary)			X		X	X	X	X	X	X	X	X	

X - Additional visit for MRI and biopsy - for PA arm only

\*2 week MRI only required for the first 5 HIFU patients in sites new to performing HIFU.

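### The standard logrank test takes detection dates as failure dates although detection schedules differ by arm, which tilts the comparison towards ablation; power is about 55% if PA failures are found only at scheduled biopsies

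*Protocol*

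**What the plan says.** - **Test.** Section 10.3: "Time to primary treatment failure will be analysed by standard logrank methods".
- **RP failure (section 7.8).** In this arm "primary treatment failure will be defined as a rising serum PSA level reaching" 0.2 ng/ml or more after an initial fall below 0.1 ng/ml. Failure to fall below 0.1 ng/ml, or clinical progression, also counts. Appendix B schedules PSA at 6 weeks and 3, 6, 9, 12, 18, 24, 30 and 36 months.
- **PA failure (section 7.8).** Here "primary treatment failure will be determined by a combination of repeat prostate biopsies, serum PSA levels and clinical appearance of symptoms/signs suggesting disease progression". The five scenarios that follow, and the rule on high-risk disease, are all read from biopsies. PSA is taken at the same nine visits as in RP, but no PSA value or rule classes a PA man as failed. A first positive biopsy in the treated area leads to one further HIFU treatment before failure is declared.
- **Biopsy schedule.** Section 7.6, PA list only: "Standard care includes transrectal biopsies at" twelve months, and again at three years. Appendix B restricts the biopsy row to HIFU patients, at 12 and 36 months.
- **Power (section 10.1, Stage 2).** The failure rate is taken as "25% increased to 35" per cent, with no time point. "Even allowing for a 10% drop-out rate, 800 randomised 1:1 between PA and RP would provide 80% power at" the two-sided 5% level. Nothing is said about detection timing.

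**The concern.** A logrank test compares the arms at each event time and treats the recorded date as the date of failure. That is harmless when both arms are examined on the same schedule. Here, a failure that arises in month 13 would be dated month 18 after RP and, on schedule, month 36 after PA. The difference never runs the other way, so PA appears to fail later even when it does not.

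Two things are at stake. If the treatments fail equally, the test can declare ablation better too often. If ablation is truly 10 points worse, the test can miss it. Section 10.1 says that a 10-point excess might be acceptable as the price of better quality of life, so this is the difference that the trial has to measure without a tilt.

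**Working it through.** **Inputs.** From section 10.1: 800 men, 1:1, 10% drop-out, so 800 x 0.9 / 2 = 360 per arm; rates 25% and 35%; two-sided 5%. From sections 7.6 and 7.8 and Appendix B: RP dated at 1.5, 3, 6, 9, 12, 18, 24, 30 or 36 months; PA at 12 or 36 months. Assumed, because the protocol does not say: 25% and 35% are reached by 36 months, and the hazard is constant.

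**1. The stated 80%.** For two proportions, n per arm = [1.96 x sqrt(2 x 0.30 x 0.70) + 0.8416 x sqrt(0.25 x 0.75 + 0.35 x 0.65)]^2 / 0.10^2 = (1.270 + 0.542)^2 / 0.01, about 329. Two arms and 10% drop-out give 732. With continuity correction it is 349 per arm, or 776. At 360 per arm, power is 81.4% with the correction and 83.5% without. By the Schoenfeld formula, with 360 x (0.25 + 0.35) = 216 events and hazard ratio ln(0.65)/ln(0.75) = 1.497, it is 84.3%. The stated 80% reproduces, provided that detection timing is the same in both arms.

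**2. The size of the dating gap.** PA date minus RP date for the same underlying failure time, in months:

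| Failure arises in | RP date | PA date | Gap |
|---|---|---|---|
| 0-1.5 | 1.5 | 12 | 10.5 |
| 1.5-3 | 3 | 12 | 9 |
| 3-6 | 6 | 12 | 6 |
| 6-9 | 9 | 12 | 3 |
| 9-12 | 12 | 12 | 0 |
| 12-18 | 18 | 36 | 18 |
| 18-24 | 24 | 36 | 12 |
| 24-30 | 30 | 36 | 6 |
| 30-36 | 36 | 36 | 0 |

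If failures are spread evenly within a window, the mean gap is (1.5 x 10.5 + 1.5 x 9 + 3 x 6 + 3 x 3) / 12 = 4.7 months in the first year and (18 + 12 + 6 + 0) / 4 = 9 months from 12 to 36 months.

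**3. Effect on the logrank test.** Failure times were simulated as exponential, with monthly hazard -ln(1 - p)/36, dated at the next scheduled assessment and censored at 36 months. There were 3,000 to 4,000 trials per scenario. The simulation error near 55% is sqrt(0.55 x 0.45 / 3,000), or 0.9 points. Ranges cover independent runs.

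| PA failures found at PSA visits (for-cause biopsy) | Power, 25% v 35% | False 'PA better', 25% v 25% |
|---|---|---|
| None | 54-56% | 8.3-8.9% |
| 25% | 65-67% | 5.7-6.2% |
| 50% | 74-75% | 4.2-4.8% |
| 75% | 78-80% | 2.9-3.6% |

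The nominal false rate in that direction is 2.5%. With equal 35% failure and no for-cause detection it is 17-18%.

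**4. Is detection timing the cause?** With the same schedule in both arms, logrank power is 84.6%. With both arms grouped into 0-12 and 12-36 months, it is 84-85%, and false 'PA better' is 2.1-2.8%. Comparing 36-month proportions gives 83-84%. Only the dating changed.

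**5. Other assumptions, with PA failures found only at scheduled biopsies.**
- Weibull shape 0.7 or 1.3 instead of constant hazard: power 55.6% or 51.8%.
- Rates of 25% and 35% reached only at 60 months: 49%, against 67% with equal schedules.
- Re-treatment, with only 75%, 50% or 25% of early PA failures classed at 12 months and the rest at 36: power 48%, 40% or 30%.

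**The case against.** The best case against has five parts.

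*The 55% is conditional.* This stands. A reader might take it as the power of the trial. The documents do not support that. Section 7.8 names PSA and symptoms as part of the PA determination, PSA is taken at all nine visits in PA, and the rule on high-risk disease applies at any point. For-cause biopsies are therefore plausible, and the range in the table is the honest statement. It softens the problem but does not remove it, because section 7.8 gives no PSA trigger for PA. The re-treatment allowance pushes the other way.

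*A shared underlying failure time is a modelling device.* Also true. RP and PA failure are different constructs, and section 4 words the outcome as need for whole-gland ablation and/or secondary interventions. But an intervention follows detection, so that wording does not by itself remove the gap.

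*The analysis change does not repair everything.* This stands. Suppose that 25% of PA biopsy failures are re-treated first, and that those first positive at 36 months are then never classed as failed. Failures arising after 12 months are 0.35 - (1 - 0.65^(1/3)) = 0.216 of PA men, so observed 36-month failure drops to 0.35 - 0.25 x 0.216 = 0.296. Power of the 36-month comparison is then 28%, and false 'PA better' at equal 25% failure is 23-24%. The logrank does worse (8% and 43%), but the larger loss comes from the counting rule.

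*Stage 2 is unfunded and its power will be reviewed; event dating is ordinary SAP content.* Partly right. However, the protocol itself names the test, the failure rules and both schedules, and Stage 1 men roll into Stage 2, so an SAP that follows it carries the tilt forward.

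*The 78 months.* A reader might infer from the trial period named in the lifetime economic analysis (section 10.3) that men are censored mid-follow-up at a 78-month close, which would enlarge the tilt. Section 7.9 ties the end of the trial to the last man's final visit, so that reading is not supported.

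**Conclusion.** The concern holds in conditional form. Followed as written, section 10.3 dates PA failures later than RP failures of the same timing, and the standard logrank test counts the difference in favour of ablation. The direction follows from the schedules; the size depends on how many PA failures are found between scheduled biopsies. Power runs from about 55% (none) to 78-80% (three quarters), against 80% stated and about 84% with equal schedules. False 'PA better' at equal 25% failure runs from 8-9% down to about 3%. These figures rest on 25% and 35% being reached by 36 months, 360 men per arm, near-constant hazard and no re-treatment delay. Later event times or re-treatment lower power further.

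**What to change.** In section 10.3, make the primary comparison the difference in cumulative primary treatment failure at 36 months, with 95% CI. Estimate it by an interval-censored or grouped-time method with common windows in both arms: up to and including the 12-month assessment, then to and including the 36-month assessment. Include all randomised men, count every observed failure in its window, and censor men lost without failure at their last assessment. Do not limit a window to men followed to its end, because that would discard observed failures and conflict with the intention-to-treat commitment. Keep the standard logrank as a sensitivity analysis.

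In section 10.1, give the time point for 25% and 35% and restate power for the chosen analysis.

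The cost is wording only, with no added visits or biopsies. The price is that RP failure timing within a window is not used.

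This corrects detection timing and nothing else. Sections 7.6 and 7.8 must still be reconciled on how a PA man first positive at 36 months and then re-treated is counted, since scheduled follow-up ends at that visit.
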